3.3.3 Subject Withdrawal from the Study

When a subject is withdrawn from the study after initiating treatment but prior to B cell follow-up, protocol-specified treatment requirements are discontinued and study-related visits, exams, procedures, assessments, tests and data collection are terminated after completion of an Early Endpoint Visit as detailed in Section 6.5.5, *Early Endpoint Visit*. However, individual subjects will be withdrawn from the protocol under the following conditions:

1. The subject withdraws consent.
2. The investigator or DAIT/NIAID believes it is in the best interest of the subject.
3. The study is terminated.

Subjects who are lost to follow-up will also be regarded as withdrawn from the protocol.

3.3.3.1 Procedures for Subject Withdrawal

Unless a subject withdraws consent and refuses, all subjects who are being withdrawn or elect to withdraw from the study after initiating treatment will undergo an Early Endpoint Visit as detailed in Section 6.5.5, *Early Endpoint Visit*. In addition, unless consent is withdrawn, B cell monitoring will be performed as outlined in Section 3.3.2.1, *Follow-up Requirements for All Treated Subjects, #3*.

3.3.4 Subject Replacement

Randomized subjects who withdraw from the trial prior to starting rituximab infusion will be replaced. Subjects who discontinue study treatment or withdraw from the trial after initiating the first treatment will not be replaced.

4 SELECTION OF SUBJECTS

Written informed consent must be obtained prior to the subject undergoing any study-related procedure, including screening tests and washout periods for prohibited medications, when applicable.

4.1 Inclusion Criteria

Subjects who meet all of the following criteria are eligible for enrollment into the study:

1. Subject has provided written informed consent.
2. Subject must be between the ages of 18 and 75, inclusive at the time of randomization.
3. Clinical diagnosis of systemic sclerosis (either limited or diffuse cutaneous disease).
4. Diagnosis of SSc-PAH within the past 5 years, with a mean pulmonary arterial pressure (mPAP) of ≥ 25 mmHg at entry.
5. Mean PVR of > 3 Wood units.
6. Screening 6MWD of at least 100 meters.
7. NYHA Functional Class II, III, or IV.
8. Subject must be able to maintain O₂ saturation $\geq 90\%$ at rest (with or without oxygen). Oxygen use is permitted.
9. Subject must be vaccinated with the pneumococcal vaccine at least 4 weeks prior to initiation of therapy, unless subject was vaccinated within 5 years of study entry. If vaccination occurred greater than 5 years prior to study entry, the subject must be revaccinated at least 4 weeks prior to initiation of therapy.
10. Subjects must have been treated with background medical therapy for PAH (prostanoid, endothelin receptor antagonist, PDE-5 inhibitor, and/or guanylate cyclase stimulators) for a minimum of 8 weeks and have been on stable dose(s) of those medical therapy(ies) for at least 4 weeks prior to randomization with no expectation of change for 24 weeks after randomization.

4.2 Exclusion Criteria

Subjects who meet any of the following criteria are disqualified from enrollment in the study:

1. Documented PAH for greater than 5 years at the time of randomization defined as:
 - Measurement of a mPAP > 25 mmHg by right heart catheterization (RHC) at least 5 years previously, OR
 - Treatment with targeted background PAH therapy for > 5 years.
2. Pulmonary Capillary Wedge Pressure (PCWP) > 15 mmHg or Left Ventricular End Diastolic Pressure > 15 mmHg.
3. Persistent hypotension with systolic blood pressure (SBP) < 90 mmHg.
4. Treatment with cyclophosphamide within 4 weeks of randomization.
5. Treatment with immunocompromising biologic agents (including, but not limited to TNF inhibitors, anakinra, abatacept, and tocilizumab) within 4 weeks prior to treatment initiation or treatment with infliximab within 8 weeks prior to treatment initiation.
6. If being treated with a non-biologic immunosuppressive or immunomodulating drug (including, but not limited to, methotrexate, azathioprine, mycophenolate, cyclosporine, hydroxychloroquine, penicillamine, and/or prednisone at ≤ 10 mg daily), changes in dosage within 4 weeks prior to randomization. Subjects taking prednisone or equivalent corticosteroid > 10mg daily are excluded.
7. Previous exposure to any lymphocyte depleting agent (Campath, ATG, etc.).
8. Prior treatment with rituximab or other B cell depleting agents.
9. PAH for any reason other than SSc including congenital heart disease, coronary left heart disease, chronic obstructive pulmonary disease, chronic thrombotic and/or embolic pulmonary vascular disease, or sleep apnea.
10. History of coronary artery disease, with any of the following events within 3 years of randomization: significant ventricular tachy-arrhythmia, stent placement, coronary artery bypass surgery, and/or myocardial infarction (MI).
11. Moderate or severe interstitial lung disease as characterized by a total lung capacity (TLC) of < 70% predicted, except if TLC is between 60-70% predicted and an HRCT within the 6 months prior to randomization shows only mild ILD.
12. Chronic infections including, but not limited to, HIV, tuberculosis (TB), hepatitis B (HBV) or hepatitis C (HCV), or chest X-ray (CXR) findings consistent with TB or latent fungal infection.
13. Positive serology for hepatitis B defined by positive HBV surface antigen and/or positive HBV core antibody, total.
14. Positive serology for HCV antibody.
15. A deep space infection within the past 2 years (including, but not limited to, meningitis, epiglottitis, endocarditis, septic arthritis, fasciitis, abdominal or pleural abscess, or osteomyelitis).
16. Evidence of active infection requiring IV or PO antibiotics within 2 weeks of randomization.
17. At or within 30 days of screening,
 - history of or current positive purified protein derivative tuberculin skin test (PPD) (> 5mm induration, regardless of Bacille Calmette Guerin [BCG] vaccine administration), or positive QuantiFERON®-TB Gold In-Tube Test (QuantiFERON®), or historical chest x-ray unless completion of treatment has been documented for active TB

- latent TB (a positive test, a negative chest x-ray, and no symptoms or risk factors), unless one month of prophylaxis has been completed prior to inclusion
 - an indeterminate QuantiFERON® unless followed by a subsequent negative PPD or negative QuantiFERON® as well as a consultation with and clearance by local infectious disease (ID) department.
18. Significant renal insufficiency defined as:
 - Estimated creatinine clearance < 40 mL/min (using Cockcroft-Gault formula based on actual body weight); OR
 - Active, untreated SSc renal crisis at the time of enrollment.
 19. Recent administration of a live vaccine (< 8 weeks) or any other immunization within 4 weeks of treatment.
 20. History of anaphylaxis or IgE-mediated hypersensitivity to murine proteins or any component of rituximab.
 21. Pregnancy.
 22. Lactation.
 23. History of malignancy within the last 5 years, except for resected basal or squamous cell carcinoma, treated cervical dysplasia, or treated in situ cervical cancer Grade I.
 24. A woman of childbearing potential (not post-menopausal or surgically sterile) who is unwilling to use a medically acceptable form of birth control (including, but not limited to, a diaphragm, an intrauterine device (IUD), progesterone implants or injections, oral contraceptives, the double-barrier method, or a condom) throughout the duration of the study.
 25. History of non-compliance with other medical therapies.
 26. A history of alcohol or drug abuse within 1 year of randomization.
 27. Receipt of any investigational drug or device within 4 weeks before the screening visit, with the exception of investigational prostanoids, endothelin receptor antagonists, PDE-5 inhibitors, and guanylate cyclase stimulators.
 28. Recipient of lung transplant.
 29. Laboratory parameters at the screening visit showing any of the following abnormal results:
 - Transaminases > 2x the upper limit of normal (ULN) and/or bilirubin > 2x ULN.
 - Absolute neutrophil count (ANC) < 1,500/mm³ (or < 1.5 x 10⁹/L).
 - Platelet count < 100,000/mm³ (or < 100 x 10⁹/L).
 - Hemoglobin < 9 g/dL.
 30. Concurrent treatment in a clinical research study using a non-FDA approved agent, with the exception of an open-label study/study extension of investigational prostanoids, endothelin receptor antagonists, PDE-5 inhibitors, and guanylate cyclase stimulators, provided the open-label investigational drug will be available and dose will remain stable through the ASC01 primary endpoint time point of 24 weeks after randomization in ASC01.
 31. Any condition or treatment, which in the opinion of the investigator, places the subject at unacceptable risk as a participant in the trial.

4.2.1 Coenrollment Guidelines

While participating in ASC01, participating in observational registries or cohorts is permitted. Subjects may not be enrolled in another clinical trial, except as noted in Exclusion Criterion #29. For any co-enrollment in studies, the combined blood volumes must not exceed the NIH policy limit nor may the objectives or procedures confound the ASC01 study endpoint assessment.

5 TREATMENT OF SUBJECTS

5.1 Description of Rituximab

5.1.1 Product Description

Rituxan® (rituximab) is a genetically engineered IgG1 kappa chimeric murine/human monoclonal antibody containing murine light- and heavy-chain variable region sequences and human constant region sequences. The chimeric antibody is produced by mammalian cell (Chinese Hamster Ovary) suspension culture in a nutrient medium containing the antibiotic gentamicin. Gentamicin is not detectable in the final product. Rituximab is composed of 1,328 amino acids, and has an approximate molecular weight of 145 kilo Dalton (kD) [116]. The antibody reacts specifically with the CD20 antigen found on the surface of malignant and normal B cells, and established B cell lines. Studies have shown that rituximab binds via its Fc domain to human complement and lyses lymphoid B cell lines by complement-dependent cytotoxicity through the induction of apoptosis and via antibody-dependent cell-mediated cytotoxicity [118].

The drug is manufactured by Genentech, Inc. and by Biogen IDEC, Inc. Rituximab is supplied as a sterile, clear, colorless, preservative-free liquid concentrate for intravenous (IV) administration in either 100 mg (10 mL) or 500 mg (50 mL) single-use vials, which must be diluted before administration [116].

5.1.2 Packaging and Labeling of Study Product

Rituximab labeled for investigational use will be provided without charge by Genentech, Inc. or IDEC Pharmaceuticals. The sponsor of the trial will ensure maintenance of complete and accurate records of the receipt, dispensation, and disposal or return of all trial drugs in accordance with Title 21 CFR Parts 312.57 and 312.62 and with Genentech/IDEC requirements.

Placebo will be supplied in packaging identical to rituximab.

5.1.3 Storage and Handling of Study Product

Rituximab vials will be stored in a refrigerator at 2° to 8°C (36° to 46°F). Rituximab will not be used beyond the expiration date stamped on the carton and printed on the vial. Rituximab vials will be protected from direct sunlight. The product will not be frozen or shaken.

After dilution to 1-4 mg/mL in normal saline, rituximab is physically and chemically stable at 2° to 8°C (36° to 46°F) for 24 hours, and subsequently for 24 hours at room temperature provided that dilution has taken place in controlled and validated aseptic conditions. It is strongly recommended that higher concentrations of rituximab (4 mg/mL) be used for this patient population in order to minimize fluid administration.

Placebo will be handled in the same fashion as described above.

5.2 Dosage Regimen

Rituximab (1000 mg) or placebo will be administered as 2 infusions given 2 weeks apart.

5.3 Administration of Rituximab

The following drugs, safety equipment, and supplies must be available during the rituximab infusions:

- Oxygen
- Oral and endotracheal airways and intubation equipment
- Epinephrine 1:1000 solution for IV or endotracheal injection
- Antihistamines
- Corticosteroids
- IV infusion solutions, tubing, catheters, and tape
- Defibrillator with electrocardiogram (ECG) monitor
- Dopamine
- Atropine
- Bronchodilators

Patients will be closely monitored during the infusions. Guidance for monitoring for infusion reactions includes continuous heart rate monitoring during the infusions, with capability to detect early bradycardia. Vital signs should be monitored frequently as suggested below. During the first infusion, vital signs should be checked every 10 minutes during infusion for the first hour, and then every 15 minutes until the subject is discharged 1 hour after the infusion, or as clinically indicated. For the second infusion, vital signs should be checked every 15 minutes during infusion for the first hour, and then every 30 minutes until the subject is discharged 30 minutes after the infusion, or as clinically indicated. Systolic and diastolic pressures should be monitored, with mean arterial pressures (MAP) monitored as clinically indicated. Oxygen saturations should be measured at baseline and then every 30 minutes or as clinically indicated. Study centers may defer to local institutional standards of practice for monitoring hemodynamic and pulmonary status.

Patients with significant PAH typically do not have systemic hypertension, but rather have low blood pressures. Because transient hypotension may occur during rituximab infusion, it is necessary to anticipate an exacerbation of baseline hypotension. Persistent hypotension with a SBP < 90 mmHg is an exclusion criterion for this study. If after randomization on the

day of rituximab administration prior to beginning the infusion the subject's systolic BP is < 90 mmHg or, if measured/calculated, the MAP is < 55 mmHg, then the guidance in **Figure 6**'s algorithm below is recommended. To summarize, for a SBP < 90 mmHg or MAP < 55 mmHg prior to starting the infusion a fluid bolus of up to 500 cc normal saline (NS) may be administered. If the pressures remain below these parameters and the physician is worried about hypotension then the infusion should not be given and the subject should be sent home. Another attempt to infuse the study drug may be made within 3 days. If on the second attempt the subject's BP remains too low in the opinion of the investigator, then he/she will be withdrawn from the study. PAH specific medications should not be withheld to increase the blood pressure. In summary, study centers may defer to local institutional standards of practice for subject monitoring and clinical management during study drug infusions.

Patients with Class IV or advanced Class III symptoms should receive close nursing attention (preferably 1:1 care) during the infusion. These patients are at high risk for hemodynamic compromise should they suffer a hypersensitivity reaction. Therefore, each participating institution will have an established algorithm for acceleration of care should a patient hemodynamically decompensate. It is essential that a code team can rapidly and directly respond to the patient's hemodynamic deterioration and immediately transfer the patient to an inpatient unit for accelerated care (i.e. an off-site infusion center would not be appropriate for these patients).

Research coordinators will contact subjects by phone within 24 hours after discharge from the infusion center to assess for adverse events.

[figure not shown]

Figure 6. Guidance algorithm for managing hypotension during rituximab infusion.

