3.3.2.1 Follow-up Requirements for All Treated Subjects

Independent of whether treated subjects have completed the full course of rituximab, the following procedures will apply:

1. If prohibited medications as defined in Section 5.6, *Prohibited Medications and Treatments* are not needed for treatment of progressive PAH, the subject will complete all scheduled study visits including all exams, procedures, assessments, and tests according to the protocol.
2. If prohibited medications as defined in Section 5.6, *Prohibited Medications and Treatments* (i.e. addition of new or a change in the dose of background PAH therapies [prostanoid, endothelin receptor antagonist, PDE-5 inhibitor, and/or guanylate cyclase stimulators] or surgical therapy) are needed for treatment of progressive PAH prior to the Week 24 visit, or if the subject withdraws consent, he/she will be asked to complete an Early Endpoint Visit as detailed in Section 6.5.5, *Early Endpoint Visit*.
3. In addition, if the subject has not withdrawn consent and has not achieved B cell recovery, follow-up clinical care must include visits at least quarterly to monitor recovery of B cells. Quarterly monitoring visits will continue until B cell recovery or for 2 years after initial treatment (whichever occurs first). Recovery is defined as the time point at which B cells recover to within 10% of baseline levels; if a baseline value is not available then recovery is defined as a B cell level of at least 90% of the lower limit of normal. During this monitoring period, AEs and SAEs will be assessed, providing the subject has not withdrawn consent, to capture any infectious event \geq Grade 3 using the NCI-CTCAE. No additional study-related data will be collected.

Subjects who have discontinued their concurrent medications prior to Week 24 for toxicity only, and not disease progression, will continue to participate in the study. They will be permitted to change medication for PAH in order to maintain control of their disease and will complete all exams, procedures, assessments, and tests according to the protocol.

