5.3.5 Criteria for Permanent Discontinuation of Rituximab Infusion

If a subject experiences any of the events listed below, rituximab infusions will be discontinued, and procedures for discontinuation of protocol-specified treatments and follow-up will be implemented (as per Section 3.3.2.1, *Follow-up Requirements for all Treated Subjects*):

- Syndrome resembling tumor lysis syndrome
- NCI-CTCAE Grade 3 (severe) hypersensitivity reaction
- NCI-CTCAE Grade 3 or higher (severe/life-threatening) cytokine release acute infusion reaction
- NCI-CTCAE Grade 3 or higher (severe/life-threatening) cardiac arrhythmias. In addition, see Protocol Section 3.3.2, *Discontinuation of Protocol-Specified Treatment Requirements* for significant cardio-pulmonary disease progression events warranting discontinuation of protocol-specified treatment requirements.
- NCI-CTCAE Grade 3 or higher (severe/life-threatening) mucocutaneous reactions

- Significant hypotension during the infusion not responsive to standard medical intervention
- Events listed in Section 3.3.2, *Discontinuation of Protocol-Specified Treatment Requirements*

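### Protocol 5.3 withdraws a subject from the study for persistent low blood pressure before an infusion without limiting this to the first infusion; for a once-dosed subject that conflicts with 3.3.2.1

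*Protocol*

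**What the plan says.** Protocol 5.3 covers both infusions; it sets vital-sign schedules for each. Its hypotension rule is triggered by a systolic pressure below 90 mmHg or a mean arterial pressure below 55 mmHg on the "day of rituximab administration prior to beginning the infusion". A fluid bolus may be given. If the pressure stays low and the physician is concerned, the subject goes home and a second attempt may be made within 3 days. If pressure is still too low then, "in the opinion of the investigator, then he/she will be withdrawn from the study".

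Protocol 3.3.2.1 opens: "Independent of whether treated subjects have completed the full course of rituximab, the following procedures will apply". Its item 1 says that, if no prohibited medication is needed for progressive PAH, "the subject will complete all scheduled study visits including all exams, procedures, assessments, and tests according to the protocol". Item 2 sends a subject to an Early Endpoint Visit if prohibited PAH treatment is needed before Week 24 or consent is withdrawn.

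Study withdrawal has defined consequences. Under 3.3.3, "assessments, tests and data collection are terminated after completion of an Early Endpoint Visit". Under 3.3.3.1, "all subjects who are being withdrawn or elect to withdraw from the study after initiating treatment will undergo an Early Endpoint Visit". Under 3.3.4, "Subjects who discontinue study treatment or withdraw from the trial after initiating the first treatment will not be replaced".

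**The concern.** Suppose a subject has received infusion 1 and is persistently hypotensive before infusion 2. Section 5.3 ends that subject's participation, while 3.3.2.1 keeps the subject in every scheduled visit. Low pressure before an infusion meets neither exception in 3.3.2.1, so a site cannot follow both sections.

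At stake is on-study follow-up of an exposed, haemodynamically fragile subject who cannot be replaced. One omitted dose becomes loss of the primary endpoint assessment and of most routine safety collection, when omitting the dose would be enough.

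**Working it through.** The plan gives no figure on this point, so there is none to reproduce. The check compares the text, then the timing, then the precision.

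**Does the rule reach infusion 2?**
- Section 6.5.3.2 (Week 2 visit) refers staff to Section 5.3 for infusion procedures.
- Section 5.3.1 concerns each infusion and sends hypotensive patients to 5.4.3.2 and Figure 6.
- Section 5.3.6 repeats the 3-day return for hypotension and ties it to time windows given for both infusions.

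Nothing in the text restricts the rule to Day 0.

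**How do neighbouring rules treat a treated subject?**

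| Situation | Section | Consequence |
|---|---|---|
| Infusion 2 not given within 2-4 weeks of infusion 1 | 5.3.6 | Second infusion omitted |
| "Significant hypotension during the infusion not responsive to standard medical intervention" | 5.3.5 | Infusions stopped; follow-up under 3.3.2.1 |
| Pressure unstable during an infusion | 5.4.3.2 | Clinical judgement on stopping; follow-up under 3.3.2.1 |
| Pressure still low before the re-attempt | 5.3 | Withdrawn from the study |

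The last row is the harshest, although the subject has not been given the dose in question. The conditions in 3.3.3 are withdrawn consent, best interest of the subject, and study termination; loss to follow-up also counts as withdrawal. None makes an omitted dose automatic withdrawal.

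**Timing.** Visit 4 is Day 14 ± 4 (6.5.3.2), so the latest on-schedule first attempt is Day 18. The re-attempt is within 3 days: 18 + 3 = Day 21. The Week 4 window is Day 28 ± 7, that is Days 21-35 (6.5.4.1). The two touch only at Day 21, so the Week 4 walk is probably lost. A later withdrawal, up to Day 28, requires infusion 2 to have been delayed already for another reason.

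**Walks.** Post-baseline walks are scheduled at Weeks 4, 12, 24, 36 and 48. Withdrawal before the Week 4 walk loses 3 of 3 through Week 24 and 5 of 5 through Week 48. If the Week 4 walk was already done, the losses are 2 of 3 and 4 of 5. One Early Endpoint walk is gained.

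**Safety follow-up.** Section 7.3.2 collects Grade 2 and higher events until 30 days after withdrawal. For withdrawal on Day 21 that is 21 + 30 = Day 51, against 48 × 7 = Day 336 for a completer. Afterwards, collection is limited to Grade 3 and higher infections while B cells remain unrecovered (3.3.2.1 item 3).

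**Precision.** The documents give no variance components, so these are assumptions: 30 subjects per arm; walks at Weeks 0, 4, 12 and 24; fixed effects for treatment, week, week squared and treatment by week; random intercept SD 100 m; no intercept-slope correlation; the same components in both arms; residual SD 15, 25, 35 or 40 m. The slope SD is set so that the SD of the Week 24 change equals the protocol's 58 m:

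24² × (slope SD)² + 2 × (residual SD)² = 58².

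At residual SD 25 m this gives √(3364 − 1250)/24 = 1.92 m per week. The contrast is 24 times the treatment-by-week coefficient, with its standard error from generalised least squares. One subject's record is then replaced by a shortened one.

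- Baseline plus one Early Endpoint walk on Day 14, 18, 21 or 28: the standard error rises 0.71% to 0.84%. At residual SD 25 m and Day 14 it goes from 14.573 to 14.695 m (14.695/14.573 = 1.0084).
- Baseline, a Week 4 walk on Day 21 or 24, and an Early Endpoint walk on Day 28 (the delayed case): it rises 0.69% to 0.82%.

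**The case against.** The strongest reply is that the rule was written for Day 0. The preceding sentence in 5.3 recalls that persistent hypotension is an exclusion criterion, and the rule opens by referring to the period after randomisation. That reads as eligibility text, and it fits 3.3.4 and 8.2.2, where randomised subjects who withdraw before dosing are replaced and left out of ITT. The passage also summarises Figure 6, which is not available and might carry a first-infusion limit. It is framed as recommended guidance, and it lets centres defer to local practice.

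This makes a Day 0 intent plausible, and it is why the point is a conflict on literal reading and not a demonstrated intention. It does not remove the conflict. The limit is not in the text, and the deference to local practice concerns monitoring and clinical management, not whether a subject remains in the study.

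Two further replies carry less weight. Section 5.3.6 gives a milder result for infusion 2, but it is a dosing-window rule and does not override an instruction to withdraw. Section 3.3.3 allows withdrawal in the subject's best interest, but that is a separate judgement. In 5.3 the investigator judges only the blood pressure, and withdrawal then follows automatically.

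One reply stands in full. A reader might infer that the rule exposes a hypotensive subject to an extra catheterization, and cite the 1.1% serious adverse event rate (76 of 7218 procedures) in 5.9. The documents do not support that. The Early Endpoint Visit before Week 24 includes the Week 24 catheterization (6.5.6), and a subject who stays in the study has that procedure at Week 24 anyway (6.5.4.6). There is one post-baseline catheterization either way. Section 6.5.6 also says subjects will be asked to attend, which is softer than 3.3.3.1. What remains is that the procedure is moved to an uninformative early time.

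**Conclusion.** Wrong as written, at the lowest severity. For a subject who has received infusion 1, the literal rule in 5.3 cannot be followed together with 3.3.2.1, and it is out of line with 5.3.5, 5.3.6 and 5.4.3.2. If Figure 6 contains a first-infusion limit, the text of 5.3 still needs to state it.

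The consequence is limited. The number affected is not in the documents and is probably small. The precision cost is below 1% per subject and rests on the assumed components. A reader might go further and infer lost power, a biased treatment estimate, or removal from the primary analysis. None of these follows. Protocol 8.2.2 keeps the subject in ITT. Protocol 8.5.5 and SAP 7.2.2 bring the early walk into the model. B-cell monitoring continues unless consent is withdrawn, and two-year vital status is still sought. Whether an early catheterization enters the PVR model is unclear from SAP 7.1.2 and 7.3.1, so no loss of PVR data is claimed.

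**What to change.** State in 5.3 that study withdrawal for persistent pre-infusion hypotension applies only to randomised subjects who have received no study drug. A subject who has received any study drug omits the second infusion and continues all scheduled visits under 3.3.2.1 item 1, unless item 2 or a condition in 3.3.3 applies. Check Figure 6 and align it.

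The cost is one sentence in an amendment and a check of the figure. Blood pressure thresholds and infusion decisions do not change. The retained visits are already in the schedule, and the catheterization stays at Week 24.
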